### **Placebo Arm**

Participants randomized to the placebo arm will receive matching carbonated lemon water 296 mL PO once to be taken within a 4-hour period, (about 10 oz.) and 2 over-encapsulated microcrystalline pills capsules twice daily for six days or until discharge, whichever is earlier. The placebo will be flavored to match the taste of the interventional arm.

## **4.4 Co-Interventions**

This trial will control the use of magnesium citrate plus the probiotic Floranex vs placebo during the intervention period. Enrolled participants will not receive open-label magnesium citrate or the probiotic Floranex during the intervention period. All other treatment decisions will be made by treating clinicians without influence from the protocol. Administration of other antiviral medications (“rescue therapy”) will be allowed. The decision to administer other antiviral medications will be made by treating clinicians and will be recorded in the case report form. The decision to administer immunomodulating medications, including corticosteroids, will be made by treating clinicians and will be recorded in the case report from.

## **4.5 On-Study Monitoring**

All patients enrolled in the study will be initially hospitalized and will therefore receive monitoring as a part of routine clinical care, including monitoring by their physicians, nurses, respiratory therapists, and ancillary staff.

Study personnel will review the electronic health record daily for new potential medication interactions with magnesium citrate (see Appendix B). If a medication that is considered to be contraindicated with magnesium citrate or the probiotic Floranexs is discovered, treating clinicians will be contacted to discuss if stopping study drugs is appropriate or if the medication in question can be stopped or substituted. If a medication with a potential interaction with magnesium citrate or the probiotic Floranex is identified, study personnel will contact treating clinicians to ensure they are aware of the potential interaction. Treating clinicians will determine whether an alternative medication would be appropriate or whether the risk-benefit ratio favors continuing the medication with the known potential interaction.

In addition to manual monitoring by study personnel for medication interactions, many electronic health records contain tools within the electronic order entry system to automatically screen for medication interactions and notify ordering providers of the potential interaction at the time of order entry.

## **4.6 Criteria for Stopping Study Drug**

Administration of the blinded study drug may be stopped temporarily or permanently for (a) adverse events, (b) results of on-study monitoring, (c) clinical deterioration, or (d) evidence of an alternative cause to the patient’s symptoms.

If a patient experiences an adverse event that the patient (or legally authorized representative), treating clinicians, or investigators feel merits temporarily or permanently stopping the study drug, the study drug will be stopped.

The explanation for stopping the study drug will be recorded in the case report form, and the adverse event will be recorded and reported according to the adverse event guidelines below. If the adverse event resolves to the extent that the patient (or legally authorized representative), treating clinicians, and investigators feel that resuming the

study drug is appropriate, the study drug will be resumed, and this information will be recorded in the case report form.

Patients on study may experience clinical deterioration due to their illness. Clinical deterioration will be defined as a decrease of 1 point or more on the ordinal scale for the primary outcome (e.g., patient transitions from “hospitalized on supplemental oxygen” to “hospitalized on non-invasive ventilation or high flow nasal cannula”). Patients who experience clinical deterioration in either group may be administered other antivirals or immunomodulators as “rescue therapy”. For patients who experience clinical deterioration for which treating clinicians feel optimal care would be to stop the study drug, unblind group assignment, and administer magnesium citrate and/or the probiotic Floranex to patients in the placebo group, the study drug will be stopped, the site investigator will contact the coordinating center to receive the unblinded study group assignment, and any additional treatment will be deferred to treating clinicians. In this situation, the following data will be recorded in the case report form: the criteria met for clinical deterioration; the reason for stopping study drug and unblinding; use of magnesium citrate, other antivirals, and immunomodulators; and study outcomes.

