### Primary Outcome

1. Change in COVID Ordinal Outcome Scale (Appendix E) through Day 7 after completion of therapy

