## 5. OUTCOMES

### 5.1 Primary Outcome

1. Change in WHO Clinical Progression Scale through Day 7 after completion of therapy

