## Appendix E

### COVID Ordinal Outcome Scale

Patient State	Descriptor	Score
Uninfected	Uninfected, no viral RNA detected	0
Ambulatory Mild Disease	Asymptomatic, viral RNA detected	1
	Symptomatic, independent	2
	Symptomatic, assistance needed	3
Hospitalized Moderate Disease	Hospitalized, no oxygen needed	4
	Hospitalized, oxygen by mask or nasal prongs	5
Hospitalized Severe Disease	Hospitalized, oxygen by NIV or high flow	6
	Intubation and mechanical ventilation, $pO_2/FiO_2 \geq 150$ or $SpO_2/FiO_2 \geq 200$	7
	Mechanical ventilation, $pO_2/FiO_2 < 150$ ( $SpO_2/FiO_2 < 200$ ) or vasopressors	8
	Mechanical ventilation, $pO_2/FiO_2 < 150$ and vasopressors, dialysis or ECMO	9
Dead	Dead	10

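### Section 4.6 defines clinical deterioration as a fall in score, but on Appendix E a fall is improvement, so the numeric rule excludes its own example (5 to 6)

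*Combined protocol and SAP*

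**What the plan says.** Section 4.6 (Criteria for Stopping Study Drug) gives four grounds for stopping the blinded drug, of which (c) is clinical deterioration. It then defines the term: "Clinical deterioration will be defined as a decrease of 1 point or more on the ordinal scale for the primary outcome". The example that follows is a patient who starts on supplemental oxygen and ends "hospitalized on non-invasive ventilation or high flow nasal cannula".

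Two provisions follow from the definition. Patients who deteriorate may receive other antivirals or immunomodulators as rescue. Where the treating clinicians also judge it to be optimal care, the drug is stopped, the assignment is released to the site investigator, and placebo patients may be given the active products. For that second route the protocol sets a documentation duty: "In this situation, the following data will be recorded in the case report form: the criteria met for clinical deterioration".

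The scale has two names. The synopsis gives the primary outcome as "Change in COVID Ordinal Outcome Scale (Appendix E) through Day 7 after completion of therapy". Section 5.1, like Section 2.4, gives it as "Change in WHO Clinical Progression Scale through Day 7 after completion of therapy". Section 7.1 analyses the Day 7 COVID Ordinal Outcome score. Appendix E is the only scoring table in the document.

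**The concern.** Appendix E scores the best state 0 and death 10, so worsening moves the score up. A definition of deterioration that requires the score to go down points the wrong way and conflicts with the example attached to it.

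The sentence is an operative rule. Section 4.4 says "Enrolled participants will not receive open-label magnesium citrate or the probiotic Floranex during the intervention period", and Section 3.7 keeps patients, clinicians, study staff and outcome assessors blinded until after database lock. The route in Section 4.6 is the exception to both, and clinical deterioration is its stated entry condition. Section 9.1.3 cites the same route as one of the ways the risk of being assigned placebo is limited. A patient properly unblinded after worsening would have to be documented against a numeric criterion that the patient does not meet.

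**Working it through.** No figure in the plan needs reproducing. The check is to score the example, and some neighbouring transitions, on Appendix E.

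**Inputs**
- Written rule (Section 4.6): change in score ≤ -1.
- Start of the example (Appendix E): "Hospitalized, oxygen by mask or nasal prongs" = 5.
- End of the example (Appendix E): oxygen by NIV or high flow = 6.
- Other Appendix E scores used: in hospital without oxygen = 4; intubated, better oxygenation band = 7; dead = 10.

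**Formula:** change = end score - start score.

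| Transition | Change | Clinical direction | Rule as written (≤ -1) | Corrected rule (≥ +1) |
|---|---|---|---|---|
| 5 to 6 (the protocol's example) | 6 - 5 = +1 | worse | not met | met |
| 6 to 7 | 7 - 6 = +1 | worse | not met | met |
| 5 to 10 (death) | 10 - 5 = +5 | worse | not met | met |
| 5 to 4 (off oxygen) | 4 - 5 = -1 | better | **met** | not met |

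Because Appendix E rises with severity throughout, every worsening is a positive change. The written criterion therefore misses all of them and is met only by improvements.

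**Could another scale make the word correct?** On a reversed score (10 minus the Appendix E value) the example would run from 5 to 4, a change of -1, and the rule would work. No such scale is printed. Sections 2.4 and 5.1 use the WHO name but give no separate table. Section 7.1 says an odds ratio above 1.0 favours active treatment; that fixes how the model result is read and does not rescore Appendix E.

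**How far the error reaches**
- Stopping grounds in Section 4.6: 1 of 4 uses the definition.
- Of the two provisions tied to it, rescue therapy does not depend on it. Section 4.4 already leaves this to clinicians with no deterioration test: "The decision to administer other antiviral medications will be made by treating clinicians and will be recorded in the case report form", and it says the same of immunomodulators. That leaves one: unblinding with open-label active drug.
- Outcomes in Section 5: 1 primary + 12 secondary + 4 safety = 17, of which 0 use the term.
- Primary-model covariates in Section 7.1: 0 of 5.
- Bayesian thresholds (efficacy, futility, harm): 0 of 3.

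**The case against.** The strongest reply is that the sentence corrects itself. The defined term means worsening and the example names an exact worsening, so a site that recorded a move from supplemental oxygen to high flow would be recording what the protocol illustrates. No clinician would seek unblinded rescue for a patient coming off oxygen, or think the rule blocked it for one moved to high flow. Stopping the drug does not hang on this definition alone: there are three other grounds, and Section 10.5 lets the treating physician or investigator withdraw a patient at any time. Magnesium citrate is given once, with a possible second bottle, so a later stop mainly affects the probiotic capsules. The documents show no case report form field or edit check that uses the sign of the change, so the recording problem is hypothetical.

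Most of this stands, and it limits the consequence. The intended meaning can be recovered, unblinding of recovering patients is unlikely, and a wrong electronic check is a possibility rather than a documented fact. The difference in scale names is a separate inconsistency and adds no weight to the direction error. What does not follow is that the text is acceptable. The numeric criterion and its example contradict each other, and the criterion is what the case report form is told to record.

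**Conclusion.** The concern holds and is minor. As written, the numeric criterion is reversed: it requires -1 or lower, while the protocol's own example is +1. The consequence is confined to the criterion for unblinding with open-label active drug, and to its documentation. No endpoint, covariate, sample-size input or stopping threshold is affected.

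The number of patients involved cannot be estimated, because the documents give no rate of deterioration or unblinding. Each unblinded patient would be 1/30 = 3.3% of the planned 30. That total could grow, since enrollment pauses at 30 and the DSMB may then allow it to continue.

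The conclusion assumes that Appendix E is the scale Section 4.6 refers to. The synopsis supports this, and no other scoring table is given.

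**What to change.** In Section 4.6, change the direction and name the scale, for example: *Clinical deterioration means an increase of at least 1 point on the COVID Ordinal Outcome Scale (Appendix E).* Keep the existing example, which then satisfies the rule (+1), as does every other one-step worsening. If any check in the electronic case report form uses this definition, align it.

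The cost is one word and a scale name: no patients, no new data and no change to the analysis. This edit leaves the WHO name in Sections 2.4 and 5.1; making the name uniform there is a separate editorial correction.

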## 5. OUTCOMES

### 5.1 Primary Outcome

1. Change in WHO Clinical Progression Scale through Day 7 after completion of therapy

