## **4. STUDY INTERVENTIONS**

### **4.1 Treatment of Study Participants**

A summary of the trial’s schedule of events is included in Appendix A.

Timing of study procedures is based on the time of randomization, which is defined as “Time 0”. The primary outcome will be assessed on Study Day 7, which corresponds to 7 days after randomization.

Study medications will be administered by clinical or research personnel while the patient is hospitalized. The study medication will be administered within 4 hours of randomization. On Study Day 1, study personnel will review patient records to confirm administration of the study drug and document the volume of magnesium citrate

and the probiotic Floranex was consumed. Research personnel will assess patients at Day 1-5, 7 and through Day 29; these assessments will be completed by phone if the patient has been discharged from the hospital.

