## **4.2 Study Arms**

### **Magnesium Citrate plus The probiotic Floranex Arm:**

Participants assigned to the magnesium citrate plus the probiotic Floranex arm will receive 1 bottle of magnesium citrate 296 mL PO once to be taken within a 4-hour period, (about 10 oz.). Because magnesium citrate remains within the intestinal lumen, a second bottle can be provided if there is limited bowel movement. Patients will be asked to take 2 capsules of the probiotic Floranexs twice daily for six days or until discharge, whichever is earlier.

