## 7. STATISTICAL CONSIDERATIONS

### 7.1 Statistical Approach

The primary analysis will be an intention-to-treat comparison of the Day 7 COVID Ordinal Outcome score between patients randomized to magnesium citrate plus a the probiotic Floranex versus placebo. This analysis will be conducted with a proportional odds model using the Day 7 COVID Ordinal Outcome score as the dependent variable, randomized group assignment as the primary independent variable, and the following co-variables: age, sex, baseline COVID Ordinal Outcome score, baseline SOFA score, and duration of acute respiratory infection symptoms prior to randomization. An odds ratio  $>1.0$  indicates more favorable outcomes with magnesium citrate plus the probiotic Floranex on the COVID Ordinal Outcome scale, while an odds ratio  $<1.0$  indicates more favorable outcomes with placebo.

In addition to reporting data for the full trial population we will also report data separately for patients randomized in the ICU (who tend to be more severely ill) and those randomized outside the ICU (who tend to be less severely ill) as well as those with duration of symptoms  $\leq 5$  days prior to randomization and those with  $>5$  days of symptoms prior to randomization.

The anticipated study size is 30 patients. We calculated the sample size under the assumption that we would have an interim analysis after approximately each 10 patients. We calculated the standard error of the log(odds-ratio) statistic with 15 patients per arm based on data from a recently completed trial within the PETAL Network that enrolled patients early in the course of critical illness, the *Vitamin D to Improve Outcomes by Leveraging Early Treatment* (VIOLET) trial. In the VIOLET trial at Day 15, 11.5% of patients had died, 5.8% were on invasive mechanical ventilation, 22.9% remained in the hospital, and the remaining had been discharged from the hospital (Table 1). We used these outcomes in VIOLET to approximate Day 7 outcomes on the COVID Ordinal Outcome scale that we may observe in this trial.

Table 1. Patient status 14 days (“Day 15”) after randomization in the VIOLET trial.

Patient Status	Percentage of patients
Deceased	11.5%
Invasive mechanical ventilation	5.8%
Hospitalized, not on invasive mechanical ventilation	21.9%
Discharged from the hospital	60.8%

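### The declared primary outcome is anchored to completion of therapy, but the plan assesses and models the Study Day 7 score from randomization, and a Day 7 call may be made up to Day 14 with no as-of-Day-7 rule

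*Combined protocol and SAP*

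**What the plan says.** The synopsis declares the primary outcome as "Change in COVID Ordinal Outcome Scale (Appendix E) through Day 7 after completion of therapy". Sections 2.4 and 5.1 keep the timing but name the scale differently: "Change in WHO Clinical Progression Scale through Day 7 after completion of therapy".

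Section 4.1 makes randomization time zero and states: "The primary outcome will be assessed on Study Day 7, which corresponds to 7 days after randomization". For follow-up it adds that "these assessments will be completed by phone if the patient has been discharged from the hospital". Section 7.1 begins: "The primary analysis will be an intention-to-treat comparison of the Day 7 COVID Ordinal Outcome score between patients randomized" to the two arms. The model is proportional odds, with the Day 7 score as the response and the baseline score among the covariates.

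Therapy has two components (4.2). Participants in the active arm "will receive 1 bottle of magnesium citrate 296 mL PO once to be taken within a 4-hour period", and a second bottle is possible. Capsules are taken in both arms "twice daily for six days or until discharge, whichever is earlier". Adherence is checked on Days 1 to 6 (6.2.1.1 and Appendix A).

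Section 6.3.1 allows the Day 7 call to patients already discharged to be made from Day 7 to Day 14, and lists the ordinal scale among its items. No reference date for a phone score appears there, in 4.1, in 7.1, in the footnote to Appendix A or in Appendix E.

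**The concern.** The declaration of the primary outcome fixes which result the trial may claim. Here it is tied to the end of treatment, while assessment and analysis are tied to randomization. The end of treatment has no stated date: one component is a single drink, and the other lasts six days or less, depending on discharge. As written, a Day 7 result could be challenged as not the declared outcome. The stopping guidance in 7.1, including the look at 20 patients, depends on the same endpoint.

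The call window is a separate matter, and it affects the data. An inpatient is scored on Day 7, but a patient at home may be scored on a state as late as Day 14. Appendix E separates symptomatic from asymptomatic patients and independent from assisted ones, and readmission or death can occur in that week, so the score can differ.

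**Working it through.** The plan gives no figure of its own on this point to reproduce. The planned size of 30 is used below but is not in dispute.

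**1. Which day is declared?** Inputs: the first bottle is given within 4 hours of randomization (4.1), the capsules are taken on Days 1 to 6 or until discharge (4.2, 6.2.1.1), and randomization is on Day 1 (6.1, Appendix A) unless noted.

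- *Study Day 7, with the six-day course finished.* Last capsule on Day 6; 6 + 1 = Day 7. Gap from the analysed day: 0.
- *Seven days from the first bottle.* Randomization as Day 1: 1 + 7 = Day 8, gap 1. Randomization as Day 0, which is what the statement in 4.1 implies: 0 + 7 = Day 7, gap 0. A second bottle is ignored here.
- *Seven days from the last capsule.* min(6, discharge day) + 7 gives Day 8, 9, 10, 11, 12 or 13 for discharge on Day 1, 2, 3, 4, 5, or 6 and later. The gap is 1 to 6 days and varies by patient. No visit, call or analysis uses this reading.

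**2. Change or score?** At a given baseline score, change equals the Day 7 score minus a constant, and 7.1 adjusts for baseline. This is a minor part of the mismatch.

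**3. Day numbering.** Section 4.1 equates Study Day 7 with 7 days after randomization. With randomization on Day 1, 7 − 1 = 6 days. The mortality outcome follows the Day 1 convention (29 − 1 = 28 days), as does the caption of Table 1 (15 − 1 = 14 days). The two conventions place the primary time point one day apart.

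**4. Call window.** 14 − 7 = 7, so a phone score may refer to a day 0 to 7 days later than an inpatient's.

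**5. How many scores come by phone?** On planning, 7.1 says: "We used these outcomes in VIOLET to approximate Day 7 outcomes on the COVID Ordinal Outcome scale". That source is a Day 15 distribution.

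- Table 1: 60.8% discharged; 0.608 × 30 = 18.2.
- Text of 7.1, which has 22.9% still in hospital where the table has 21.9%: 100 − 11.5 − 5.8 − 22.9 = 59.8%; 0.598 × 30 = 17.9.
- At half the Table 1 share (an assumption, since fewer may be home by Day 7): 0.304 × 30 = 9.1.

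So about 18 of 30 scores would come by phone on the plan's own stand-in, and about 9 of 30 at half that share. These count all phone scores, not late ones. The documents give no rate of late calls.

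**The case against.** The best defence is that the protocol has already settled the matter. Section 4.1 names the primary outcome and fixes its day, and 6.2.1.1, 6.3.1, 7.1 and Appendix A all follow it. In the secondary outcome list, a bare day number marks a study day, while the discharge outcome is written as an interval following treatment. On that usage the disputed phrase can be read as Study Day 7, with the course by then finished. This largely stands: the intended day is hardly in doubt. It does not remove the conflict in the declaration, because the phrase is undefined and appears in all three statements of the primary outcome.

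On the calls, 6.3.1 speaks of performing the Day 7 assessment, and the window may only govern when the call is placed. That is a fair reading, but the text does not state it, and a caller who scores the patient's condition on Day 14 would be following the section as written.

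A reader might infer three stronger things that the documents do not support:

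- *That the trial will analyse an outcome up to 6 days away from the declared one.* This needs the last-capsule reading, which nothing in the schedule or analysis uses.
- *That most primary scores will come from late calls.* The figure of 18 counts every phone score and is borrowed from Day 15 data in another trial.
- *That the result will be biased towards one arm.* A difference between arms would need treatment to affect who goes home before Day 7, or patients' condition after discharge. The documents give no basis for its size or direction.

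**Conclusion.** The point holds as a conflict of wording in the declared primary outcome, together with a missing scoring rule for calls. The declared day differs from the analysed day by nothing on the most natural reading, by 0 or 1 day if counted from the first bottle, and by 1 to 6 days only on a reading that no procedure uses. The disagreement between 6 and 7 days after randomization belongs to the same definition, because it sets the primary time point.

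The call rule permits a score 0 to 7 days late for any patient discharged before Day 7. Its possible reach is about 18 of 30 patients if the borrowed Day 15 distribution applied at Day 7, or about 9 of 30 under the halved assumption. The number of calls actually late, and the size and direction of any bias, cannot be derived from the documents. Correction is still warranted, because this is the primary outcome and the repair is small.

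**What to change.** 1. In the synopsis, 2.4 and 5.1, once the authors confirm that this is what they intend, state the primary outcome as the COVID Ordinal Outcome score (Appendix E) on Study Day 7, adjusted for baseline score as in 7.1. Delete the reference to completion of therapy and use one scale name throughout.
2. As part of that definition, state whether randomization is Day 0 or Day 1, and apply the choice in 4.1, 6.1 and Appendix A.
3. In 6.3.1, state that a call made between Day 7 and Day 14 records the patient's status as of Study Day 7, and record the date of the call.
4. Minor: reconcile the oxygen area-under-the-curve phrase in the synopsis aim with the declared outcome, and the contact exclusion criterion, which is set at Day 7 in the synopsis and Day 15 in Section 3.

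The cost is protocol wording plus a line in the call script or case report form, with no added visits or patients. Two limits remain. A late call relies on up to 7 days of recall. A call alone also cannot separate scores 0 and 1, which depend on viral RNA, since Appendix A schedules swabs on Days 1, 3 and 29 but not on Day 7.
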